- a. Fasting lab results at enrollment are needed to determine baseline values. Participants that were referred to a weight management clinic at any of the participating sites may have had these labs drawn as part of their routine care. These results will be abstracted from the medical record if they are within 8 weeks of consent date. However, a research blood draw will be done at enrollment if these labs were not done as part of the participant's routine care. If the consent visit takes place virtually/by mail, the participant will be expected to travel to CHLA for a baseline research blood draw.
- b. All arms will have a follow up research blood draw at months 6 and 18.
- c. Each research blood draw will collect approximately 5 mL (1 teaspoon) of blood via venipuncture that will be used for the following testing: HbA1c, Total Chol, LDL, HDL, TG, AST/ALT, Glucose and insulin.

6. All participants

*Visit 1: if consenting via mail, these procedures will be completed at the 2nd session as visit 1 will be split in 2

** Each participant will have the opportunity to earn up to \$200 in gift cards for participation in this study: up to \$50 for participation in the intervention at 3 and 6 months and \$50 for going to the last 2 study visits (at 12 and 18 months). The amount of payment will be based upon how much of the intervention the participant completes.

***Visit 2 and 3 must occur within a 4-week period (+/- 2 weeks from the 3- or 6-month date) and Visits 4 and 5 must occur within an 8-week period (+/- 4 weeks from the 12- or 18-month date).

Study Visit Schedule for Group 3 (In-Clinic) (total visits = 9)

*Visit 1: if consenting via mail, these procedures will be completed at the 2nd session as visit 1 will be split in 2

The youth participants in this group will also earn up to \$50 at 3 months (visits 4) and 6 months (visit 7) for participation in the 6-month intervention and \$50 for completion of study visits 8 and 9.

The table below depicts the assessment time points and key measures.

Month	0	3	6	12	18
Covariates					
Co-Morbidities, race/ethnicity, household composition, socioeconomic status, and previous weight loss programs completed	x				
Primary Outcomes (Aim 1)					
Height, Weight, zBMI, %BMIp95	x	x	x	x	x
Secondary Outcomes / Mediators (Aims 2, 3)					
Youth Surveyed: Yale Food Addiction Scale-Children	x	x	x	x	x
CES-D	x	x	x	x	x
Perceived Stress Score	x	x	x	x	x
BRIEF 2	x				
ASRI	x	x	x	x	x
Food Craving Questionnaire	x	x	x	x	x

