This study will enroll 292 patients and equally allocate into 3 groups. All these calculations utilize an estimate of standard deviation of change based on the conservation of correlation of 0.5 between pre and post measurements within each group, based on Analysis of Variance (ANOVA) with two-sided Type I error of 5%. For the first study aim, the difference in the mean change of zBMI and %BMIp95 between baseline, 6 months, and 18 months across App+Coach, App, and Clinic, this study has at least 83% power to detect the effect size of 0.244 with the variance of the group means of 0.0003 for the mean change of zBMI and at least 89% power to detect the effect size of 0.263 with the variance of the group means of 2.903 for the mean change of %BMIp95. For the second study aim, the difference in zBMI and %BMIp95 mean change between App+Coach and Clinic, based on two sample t-test with two-sided Type I error of 5%, this study has 88% to detect an effect size of 0.580 corresponds to the mean difference of pre and post change in zBMI at least 0.040 standard deviation between the two groups and a 92% power to detect an effect size of 0.625 corresponds to the mean difference of pre and post change in %BMIp95 at least 4.08 percent between the two groups. For the third study aim, the difference in zBMI and %BMIp95 mean change between App+Coach and App, based on two sample t-test with two-sided Type I error of 5%, this study has 71% power to detect an effect size of 0.464 corresponds to the mean difference of pre and post change in zBMI at least 0.032 standard deviation between the two groups and a 68% power to detect an effect size of 0.452 corresponds to the mean difference of pre and post change in %BMIp95 at least 2.80 percent between the two comparison groups. Assuming 20% dropout rate, this study will achieve the desired study power of 80% for study aim 1 and 2. (nQuery + nTerim 4.0 and Stata/SE 15.1).

Statistical Analysis

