Statistical analysis: All statistical analyses were conducted in accordance with the planned study protocol.¹⁹ We estimated that 180 participants (60 in each group) would provide 89% power ($\alpha = 0.05$, 2 sided), to detect an effect size of 0.29 which corresponds to a difference of 4.0% %BMIp95 between the three groups. Analyses followed principles of intention-to-treat (ITT) and were performed in nQuery + nTerim 4.0 and Stata/SE 17 (StataCorp, College Station, TX). A two-sided significance level of 0.05 was utilized throughout the analyses. Our analysis approach is based under the assumption that data are missing at random, therefore, imputation using last observation was carried forward, and multiple imputation based on logistic regression model (for BEDS-7 scores only) were utilized to account for missing data. Results from the ITT analysis using imputation were compared as per protocol analysis with completed data. For all outcomes a per-protocol analysis was conducted for: full-program (completed full 24-week intervention period), pre-COVID (completed 24-week intervention prior to 3/15/2020), and during COVID (completed 24-week intervention after 3/16/2020). In addition, to account for impacts of the intervention dosage received on each primary outcome measure we conducted an analysis of participants who were adherent to at least 80% of the prescribed intervention modalities versus those who were nonadherence. Participants' demographic characteristics and baseline anthropometric measurements were reported as appropriately, mean and standard deviation or median and interquartile range for continuous variables, and frequency and percentages for categorical variables. The change in %BMIp95 between week 24 and baseline was assessed using analysis of variance (ANOVA) for all participants via ITT, per-protocol, PreCOVID and during COVID. First, the %BMIp95 was analysed in log scale mixed-effects linear regression model to assess the association between change in %BMIp95 and demographic characteristics (sex, ethnicity,

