obesity related co-morbidities), CED-SC, PSS, BRIEF-2, YFAS-c, and BEDS-7 scores univariately and adjusting for recruitment site as a covariate. Then, a multivariable mixedeffects linear regression model was utilized to examine the effect of the possible factors on change in %BMIP95 accounting for recruitment site, demographic and other measured characteristics. The results are expressed in percent change with its associated 95th% confidence interval and p-value.

Data management and quality assurance

Principles underlying our approach to quality control includes: (1) standardization of measurements; (2) use of clear and specific protocols for all study activities including training for data collection and processing; (3) validation and verification of data management procedures by using of software capable of checking for out-of-range values and other sources of outliers; (4) implementation of a data cleaning protocol; and (5) periodic meetings and progress reports to provide specific, well-documented feedback to the investigators concerning potential difficulties as well as sufficient follow-up to ensure that problems are resolved in a timely fashion. Confidentiality will be strictly maintained during all data management. Children's Hospital of Los Angeles Biostatistics Core, Saban Research Institute, will follow aforementioned schemes to collect and manage with maintaining consistent quality and security of the study observations.

Data Collection Management Plan AppCoach:

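### The arm comparison of week-24 change in %BMIp95 omits the baseline value; adding it costs almost nothing and buys a low-to-moderate gain in precision, not a correction of bias

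*Combined protocol and SAP*

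**What the plan says.** The Statistical Analysis section gives the arm comparison in one sentence: "The change in %BMIp95 between week 24 and baseline was assessed using analysis of variance (ANOVA) for all participants via ITT". It names no covariate. The same section says that missing data were handled partly by "imputation using last observation was carried forward".

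Power and Sample Size Estimates uses unadjusted tests as well. For the third aim, AppCoach versus App on zBMI, it says "based on two sample t-test with two-sided Type I error of 5%, this study has 71% power to detect an effect size of 0.464"; the matching figure for %BMIp95 is 68% at an effect size of 0.452. The SD of change is based on a "correlation of 0.5 between pre and post measurements within each group". On the power goal it says: "Assuming 20% dropout rate, this study will achieve the desired study power of 80% for study aim 1 and 2". It makes no such claim for aim 3.

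The mixed-effects models at the end of Statistical Analysis relate change in log %BMIp95 to demographic and questionnaire factors, first "univariately and adjusting for recruitment site as a covariate", then in a multivariable model "accounting for recruitment site, demographic and other measured characteristics". Neither description names arm or baseline %BMIp95.

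The baseline values exist: the table of assessment time points and key measures lists "Height, Weight, zBMI, %BMIp95" at month 0 and at every later visit. The Outcomes section makes both zBMI and %BMIp95 primary.

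**The concern.** Arms will differ somewhat at baseline by chance, and baseline BMI status predicts later BMI status. Subtracting the baseline value removes its influence completely only if the slope of the week-24 value on baseline is 1. Otherwise a linear remainder of the chance imbalance stays in the estimated arm difference. ANCOVA removes that remainder, so greater precision and protection against chance imbalance are one benefit, not two.

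The comparison with most to gain is aim 3. It isolates the effect of coaching, which the background section says the pilot work could not separate from the app, and its stated power is the lowest. Using a covariate already in the dataset is an obvious step there, provided its value is not overstated.

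**Working it through.** **Inputs from Power and Sample Size Estimates.** Two-sided alpha 0.05; pre/post correlation ρ = 0.5; aim 3 difference 2.80 at effect size 0.452 (%BMIp95) and 0.032 at effect size 0.464 (zBMI); 292 enrolled; 20% dropout. Statistical Analysis gives 180 participants, 60 per arm.

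**1. Reproduce the plan's figures.** Two-sample t-test, noncentral t, unadjusted:

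| Comparison | d | Stated | n = 60 per arm | n = 78 per arm |
|---|---|---|---|---|
| Aim 2, zBMI | 0.580 | 88% | 88.3% | 94.9% |
| Aim 2, %BMIp95 | 0.625 | 92% | 92.4% | about 97% |
| Aim 3, zBMI | 0.464 | 71% | 71.3% | 82.1% |
| Aim 3, %BMIp95 | 0.452 | 68% | 69.0% | 80.1% |

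The stated powers are therefore unadjusted change-score powers at about 60 per arm. (78 per arm is 292 × 0.8 / 3 = 77.9.)

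**2. Variance saving.** With equal pre and post SDs s:
- change score: 2s²(1 − ρ)
- ANCOVA: s²(1 − ρ²)
- difference: s²(1 − ρ)², the part due to chance baseline differences
- ratio: (1 − ρ²) / [2(1 − ρ)] = (1 + ρ)/2, so the saving is (1 − ρ)/2

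**3. At the plan's ρ = 0.5.** The ratio is 0.75, a 25% saving. Replacing d by d/√0.75, with one residual degree of freedom lost, aim 3 power at 60 per arm goes from 69.0% to 80.9% (%BMIp95) and from 71.3% to 82.9% (zBMI). A simulation at 60 per arm gave a variance ratio of 0.756. Both estimators were centred on the true difference of 4.08 (means 4.07 and 4.08), so no bias is being corrected.

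**4. Is ρ = 0.5 plausible?** The SDs of change implied for aim 3 are 2.80/0.452 = 6.19 and 0.032/0.464 = 0.069. At ρ = 0.5 with equal SDs, the SD of change equals the baseline SD. A baseline zBMI SD of 0.069 is hard to believe when entry is open from the 85th percentile upward: the 85th and 95th percentiles alone are 1.645 − 1.036 = 0.61 z apart. The documents give no baseline SD, so the values below are **assumptions**. The SDs of change are held fixed and ρ = 1 − SD_change²/(2 × SD_base²):

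| Metric | Assumed baseline SD | ρ | Saving | Aim 3 power, n = 60 |
|---|---|---|---|---|
| %BMIp95 | 10 | 0.808 | 9.6% | 73.3% |
| %BMIp95 | 15 | 0.915 | 4.3% | 70.9% |
| %BMIp95 | 20 | 0.952 | 2.4% | 70.0% |
| zBMI | 0.2 | 0.940 | 3.0% | 72.5% |
| zBMI | 0.3 | 0.974 | 1.3% | 71.8% |
| zBMI | 0.5 | 0.990 | 0.5% | 71.5% |

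**5. Offsets.**
- *Carrying forward.* If a fraction m of week-24 values are baseline values carried forward, the effective correlation is m + (1 − m)ρ and the saving becomes (1 − m)(1 − ρ)/2. With m = 0.2 (assumed), 25% becomes 20%, 9.6% becomes 7.7% and 2.4% becomes 1.9%. Simulation at ρ = 0.5 gave 19.3%.
- *Estimating the slope.* The average variance cost is 1/(N − k − 2): 1/175 = 0.6% for three arms with N = 180, and 1/116 = 0.9% for two arms with N = 120. With the two-arm cost included, aim 3 power is 80.6% (ρ = 0.5) or 73.0% to 69.7% (SD 10 to 20) for %BMIp95, and 82.6% or 72.2% to 71.1% (SD 0.2 to 0.5) for zBMI. The last figure is just below the unadjusted 71.3%.
- *Degrees of freedom.* Baseline plus three site terms cost under 0.1 point of power.

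**6. Unequal SDs.** With an assumed baseline SD of 20 and the SD of change held at 6.19, post/pre SD ratios from 0.9 to 1.1 give savings between about 0% (ratio 1.05, slope about 1.00) and 21% (ratio 0.9).

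**The case against.** The strongest reply is that nothing here is an error. ANOVA on change is a legitimate estimator, and sizing a trial on an unadjusted test is ordinary and conservative. The attractive figure, about 81% to 83% power, needs a correlation of 0.5 that step 4 shows to be doubtful. At the more plausible correlations aim 3 stays below 80%, with about 4 points gained at best and a slight net loss at worst for zBMI. The one-decimal savings also depend on equal SDs. All of this stands, and it limits the claim to a modest one.

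The aim 3 shortfall is also largely a matter of sample size. The stated powers match 60 per arm, while the same section enrols 292; at 78 per arm the unadjusted test already reaches 80.1% and 82.1%. That also stands. The 292 and 180 need reconciling as a separate matter, and doing so moves power by about 11 points. It does not remove the case for a covariate that costs almost nothing at either size.

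The mixed models may partly cover the point. Baseline could enter as a repeated response or under the open-ended reference to other characteristics. But the text does not say so, and it does not name arm, so no baseline-adjusted arm difference can be read from it.

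Finally, Statistical Analysis is written in the past tense. If results are known, an adjusted analysis chosen now adds analytic flexibility. This affects how the analysis should be labelled, not whether it is useful.

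**Conclusion.** The concern holds. The plan specifies no baseline-adjusted comparison of arms for either primary metric, although the covariate is collected on everyone at month 0. The loss is of precision only: 25% of the variance at the plan's own correlation, which would bring aim 3 at 60 per arm to about 80%, but more probably 2% to 10% for %BMIp95 and 0.5% to 3% for zBMI. For zBMI the gain may be nil once the slope has been estimated.

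These lower ranges rest on assumed baseline SDs, on the plan's implied SDs of change and on equal pre and post SDs. Adjustment is worth making because it is nearly free. It does not cure the power of aim 3, and it does not repair carrying the last observation forward or the per-protocol selections. No benefit is claimed for adding site, because the documents give no between-site variance.

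**What to change.** - Compare arms by ANCOVA of week-24 %BMIp95, and separately of week-24 zBMI, on arm and the metric's own baseline value. Recruitment site, already used in the mixed models, and any randomisation strata can be further terms.
- Report the adjusted AppCoach–Clinic and AppCoach–App differences with 95% confidence intervals. Keep the unadjusted changes as description.
- State whether the multivariable mixed model contains arm and baseline %BMIp95.
- If outcome data have already been analysed, keep the ANOVA as reported and add the adjusted analysis, declared as a later addition.

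The cost is a short SAP edit and no new data. The plan names no pairwise or zBMI analysis at week 24, so the edit must spell these out as well as add the covariate. Statistically, the price is under 0.1 point of power for degrees of freedom and 0.6% to 0.9% of variance for estimating the slope.

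### The arms are tested separately in the pre-COVID and during-COVID sets with no arm-by-period term, so the plan cannot show whether the arm effect differed by period, and discordant p-values could be misread as a COVID effect.

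*Combined protocol and SAP*

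**What the plan says.** Under Statistical Analysis, the change in %BMIp95 from baseline to week 24 is assessed by ANOVA "via ITT, per-protocol, PreCOVID and during COVID". The two COVID sets are per-protocol subsets: youths who completed the 24-week intervention before 15 March 2020, and youths who completed it after 16 March 2020. The section applies this split to all outcomes. On error control it says "A two-sided significance level of 0.05 was utilized throughout the analyses".

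The mixed-effects models in the same section list sex, ethnicity, co-morbidities, questionnaire scores and recruitment site. Calendar period is not among the named terms. The only comparison between analysis sets that the section describes is the imputed ITT result against the per-protocol result. The sizes of the two COVID sets are not stated.

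**The concern.** The two COVID sets share no participants, and each is smaller than the trial. Each test therefore has less power than the full comparison. One can be significant and the other not even when the arm effect is identical in both periods.

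A difference between two p-values is not a test of a difference between two effects; that needs an arm-by-period contrast with its own standard error. The plan supplies no such contrast and no rule for reading the subset results. A report could therefore say that an arm worked only before, or only during, the pandemic without evidence for it. The protocol allows clinic sessions and study visits by WebEx, with self-reported weight at virtual visits, so readers may well ask about period. The ITT comparison itself is not affected.

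**Working it through.** **Inputs**
- Two-sided alpha 0.05 (Statistical Analysis).
- Statistical Analysis: "We estimated that 180 participants (60 in each group) would provide 89% power", "to detect an effect size of 0.29 which corresponds to a difference of 4.0% %BMIp95 between the three groups". The 0.29 is taken as Cohen's f for a three-group ANOVA.
- Power and Sample Size Estimates: "This study will enroll 292 patients and equally allocate into 3 groups", with "at least 89% power to detect the effect size of 0.263 with the variance of the group means of 2.903" for %BMIp95. Dropout is 20%.
- The 0.244 in the same section is the zBMI effect size, so it is not used here.
- Assumed, because the documents do not give it: the split between the two sets, varied from 50:50 to 80:20.

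**The plan's own power figure**

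Power = P(F > F crit), with F noncentral on 2 and N − 3 degrees of freedom and noncentrality N × f².
- N = 180, f = 0.29: 94.2%, not the stated 89%.
- N = 180, f = 0.263: 89.0%.
- N = 144 (180 × 0.8), f = 0.29: 87.9%.

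The stated 89% thus matches the other section's effect size, or roughly f = 0.29 after dropout. The result below does not depend on which was meant, so both effect sizes are carried forward.

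**Chance that exactly one set is significant, same true effect in both**

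The sets are disjoint, so with powers p1 and p2 the chance is p1(1 − p2) + p2(1 − p1).

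Example: N = 180, f = 0.29, 50:50. Each set has 90 youths and power 0.676, so the chance is 2 × 0.676 × 0.324 = 0.438.

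| Total N | f | 50:50 | 70:30 | 80:20 |
|---|---|---|---|---|
| 180 | 0.29 | 44% | 54% | 65% |
| 180 | 0.263 | 49% | 56% | 65% |
| 144 | 0.29 | 49% | 57% | 65% |
| 234 (292 × 0.8) | 0.263 | 41% | 52% | 64% |
| 292 | 0.29 | 21% | 35% | 53% |
| 292 | 0.263 | 31% | 44% | 59% |
| 180 | 0.15 | 35% | 36% | 37% |
| 180 | 0.10 | 21% | 22% | 22% |

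With no arm effect at all: 2 × 0.05 × 0.95 = 9.5%, whatever the split.

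**Interaction test under the same conditions**

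A simulation of three arms by two periods (20,000 runs, N = 180, f = 0.29, common effect) gave a significant arm-by-period F test in 5.1%, 5.0% and 4.9% of runs at 50:50, 70:30 and 80:20. Discordant subset results occurred in 44%, 53% and 65% of the same runs.

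**Precision of the interaction**

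The SD of change implied by the Power section is 4.08 / 0.625 = 6.53 (AppCoach vs Clinic) or √2.903 / 0.263 = 6.48 (three groups), so 6.5 is used. With 60 per arm split evenly, there are 30 per arm in each period:
- SE = 6.5 × √(2/30 + 2/30) = 2.37 points.
- 95% half-width = 1.96 × 2.37 = 4.65 points.
- Power for an interaction of 4.08 points: 4.08 / 2.37 = 1.72; Φ(1.72 − 1.96) is about 0.40.

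**The case against.** The strongest reply is that the plan never says the two p-values will be compared. No stated aim or outcome asks whether the arm effect changed with the pandemic. ITT is the governing principle, and the COVID sets appear beside the full-program set as further per-protocol analyses. This stands: a reader might infer that a discordant pair will be reported as a COVID effect, but the documents do not say so. What remains is that nothing in the plan prevents that reading and nothing in it could answer the question properly.

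A reader might also infer that chance alone yields discordance about half the time. As a general statement the figures do not support it. About half needs the full design effect in both periods, a total N near 144 to 180 and a split between even and about 70:30. With no arm effect the figure is 9.5%.

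Nor do the documents say that delivery shifted towards WebEx over time. They offer WebEx as an option and do not link it to COVID.

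Two practical objections also stand. Period is defined by completion date, so a randomised non-completer has none, and a model in all randomised youths needs a different definition. An interaction test would also have low power, so its main benefit is to prevent unsupported claims rather than to establish a true period difference.

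**Conclusion.** The concern holds in limited form. The plan tests the arms separately by COVID period at 0.05, with no arm-by-period term and no restriction to descriptive use, so it cannot show whether the arm effect differed by period.

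Under a common effect equal to the %BMIp95 design effect, exactly one set is significant about 44% to 65% of the time at N = 180. This rests on f = 0.263 or 0.29, the same true effect in both periods and assumed splits from 50:50 to 80:20. It falls to about 21% to 31% at N = 292 with an even split, to 21% to 37% for f = 0.10 to 0.15 at N = 180, and to 9.5% with no arm effect. The interaction test's false-positive rate is about 5%. The weakness is confined to period-specific conclusions.

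**What to change.** Replace the two stand-alone ANOVAs with one model of week-24 %BMIp95 change containing arm, period and arm-by-period.

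- **Population and period.** For all randomised youths, define period by a date that everyone has, such as the scheduled week-24 date relative to mid-March 2020. Otherwise fit the model in completers with the existing definition and say so.
- **Reporting.** Give the arm contrasts within each period and the interaction estimate, each with a 95% confidence interval. Label period-specific results descriptive, and state that no period-specific claim rests on subset p-values.
- **Timing.** The section is written in the past tense. If the analyses are already done, mark the interaction as post hoc.

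The cost is a revised model, a period definition and a few sentences in the SAP; no new data are needed. The downside is imprecision. For AppCoach vs Clinic the interaction interval is about ±4.7 points, at 60 per arm, an even split and SD 6.5. Power is only about 40% for an interaction as large as the whole 4.08-point design difference. The report should say so.

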 - x. Short form health survey form (SF-12)
 - xi. EQ5-D
 - xii. Stages of Change Questionnaire in Weight Management (S-Weight)

b. Parents:

- i. Demographic Screen
- ii. Health Encounters
- iii. Parent Satisfaction Survey

Outcomes:

	0	3	6	12	18
Study Visit Window of Completion		+/- 2 weeks	+/- 2 weeks	+/- 4 weeks	+/- 4 weeks

Covariates:

Demographic Information	x				
Youth's Perceived Stress Score	x	x	x	x	x
Family Member's BMI	x			x	x

Primary Outcomes:

BMI Status Change- %BMIf95	Height, Weight, zBMI,	x	x	x	x	x
-------------------------------	-----------------------	---	---	---	---	---

Secondary Outcomes:

Adherence-	x	x	x	x	x	
Satisfaction- Satisfaction Survey	x	x	x	x	x	
Fasting Lab Tests-	x		x		x	
Cost Analysis- Encounters*	Health Care	x	x	x	x	x

Mediators:

Addictive eating qualities- YFAS and FCQ	x	x	x	x	x
Self-Regulation- ASRI	x	x	x	x	x
Executive Function- BRIEF 2	x	x	x	x	x

*An official Health Care Encounters questionnaire will be completed by the parents at in-person/WebEx study visits at 0, 3, 6, 12, and 18 months post consent. Additionally, all participants will receive a call monthly from a study team member during the study period. In these calls weight outcomes, barriers and any interim health encounters (physician visits, diagnosis, medication prescribed etc.) occurred in the previous 4 weeks will be assessed.

3. All consenting participants:

- a. AppCoach and AppAlone arms will receive:
 - i. Loaned iPhone (app is iOS compatible only) if the participant does not already have one
 - ii. Wireless Bluetooth body weight scale
 - iii. Digital food scale
 - iv. Measuring tape (if participating virtually)
- b. In Clinic arm will receive:
 - i. Digital body weight scale
 - ii. Measuring tape (if participating virtually)
- c. Participants in the AppCoach and App arms who require an iPhone will be loaned an iPhone and accessories (including protective case), with an AT&T service plan for the 6-month intervention of the study that includes: unlimited texting, unlimited plan, unlimited voice calls to and from other cell telephones, 700 voice call minutes for calls to and from landlines, unlimited night and weekend calls to and from landlines, International calls or texts including Canada are NOT allowed and not covered. iPhones will be returned at the completion of the intervention (visit 3: 6-month follow-up visit/mail equipment back to study team).

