The primary outcome will be change in zBMI and excess BMI percent over the 95th percentile (%BMI_{p95}) compared to baseline, assessed at 3, 6, 12 and 18 months, both within the groups and compared between groups and in clinic group. For analysis over time, the Δ%BMI_{p95} (BMI percentile – 95th percentile), which is the distance (in kg/m²) from the 95th percentile, will be utilized³¹.

Secondary outcomes will include: compliance with App intervention, retention rates with scheduled phone calls and clinic visits, ASRI, BRIEF, Satisfaction survey, YFAS-c, fasting lab testing compared pre and post intervention. Collected lab studies will include: HbA1c, Lipid Panel, AST/ALT. Each of these lab tests are currently recommended for routine clinical care screening every 6-12 months in obese adolescents³.

An estimated cost analysis will be completed to determine the cost per patient to implement the 6 month AppCoach intervention, App alone intervention and multi-disciplinary in-clinic intervention (Clinic)³². Cost Analysis to include: time or expenses saved compared to in-clinic (travel, missed work or school); efficiency of clinic and staffing needs, including appointment duration and physical space requirements, and health care utilization rates and costs of care^{33, 34}.

Analytic Plan:

Power and Sample Size Estimates:

The power analysis is prepared for comparing (1) the difference in the mean change of zBMI and %BMIp95 between baseline, 6 months, and 18 months across App+Coach, App, and Clinic, (2) the difference in zBMI and %BMIp95 mean change between App+Coach and Clinic, and (3) the difference in zBMI and %BMIp95 mean change between App+Coach and App. Review of the literature revealed that the majority of studies utilize the change in zBMI to evaluate the effectiveness of weight management interventions in adolescents. However, Freedman et al. and the CDC have proposed utilizing alternative metrics for weight change such as %BMIp95 which may be more strongly associated with change in body size in adolescents. Therefore, both metrics were considered in the power calculation to further explore their use as outcome measures in youth with obesity and severe obesity.

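### The Statistical Analysis section specifies no between-arm estimate at 3, 12 or 18 months: its one arm comparison is a week-24 ANOVA, and its mixed models list no arm, visit or arm-by-visit term

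*Combined protocol and SAP*

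**What the plan says.** **What is promised.** The Outcomes section names change from baseline in zBMI and %BMIp95 as primary, "assessed at 3, 6, 12 and 18 months, both within the groups and compared between groups and in clinic group". It then introduces a distance-from-the-95th-percentile metric with the words "For analysis over time", but gives no model for that analysis. The first comparison in Power and Sample Size Estimates is "the difference in the mean change of zBMI and %BMIp95 between baseline, 6 months, and 18 months across App+Coach, App, and Clinic". AppCoach-Clinic and AppCoach-App comparisons follow, with ANOVA and two-sample t-tests as the basis for the power figures.

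**What is specified.** In the Statistical Analysis section, "The change in %BMIp95 between week 24 and baseline was assessed using analysis of variance (ANOVA) for all participants", repeated in per-protocol, pre-COVID and during-COVID subsets. The remaining models are mixed-effects regressions on the log scale. The first set relates change in %BMIp95 to sex, ethnicity, co-morbidities and the CES-D (printed CED-SC), PSS, BRIEF-2, YFAS-c and BEDS-7 scores, one at a time with recruitment site. The second is multivariable and is "utilized to examine the effect of the possible factors on change in %BMIP95", accounting for site, demographics and other characteristics. The random effect is not stated, nor whether the scores are baseline or follow-up values.

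**How the scores are labelled.** In the Outcomes table under Initial Visit, the mediator block starts with "Addictive eating qualities- YFAS and FCQ" at all five visits, followed by ASRI and BRIEF 2. PSS stands in that table as a covariate.

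**The concern.** The trial follows participants for a year after the intervention so that it can report whether any effect is maintained. That needs a between-arm estimate at 18 months, with its model, covariates and contrasts fixed in advance. If the analysis section stops at week 24, those choices are left open for a comparison that the Outcomes section calls primary.

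The mixed models are the obvious place to put a longitudinal arm comparison, but the listed terms do not provide one. Someone who fills the gap by adding arm to the existing list has a second decision to make that the text does not settle: whether YFAS-c enters as a baseline or a follow-up value. The coaching curriculum targets addictive eating directly, so follow-up YFAS-c may lie on the pathway from arm to weight. Adjusting for it would change what the arm coefficient measures.

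**Working it through.** **1. Promise against specification (between-arm, by visit)**

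| Month | Outcomes section | Power section | Statistical Analysis section |
|---|---|---|---|
| 3 | yes | no | none |
| 6 (week 24) | yes | yes | ANOVA, %BMIp95 only |
| 12 | yes | no | none |
| 18 | yes | yes | none |

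For %BMIp95, 3 of 4 times have no specified arm comparison. Counting both primary measures, 2 × 4 = 8 comparisons are promised and the section names a method for 1.

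**2. Could the mixed models supply the missing times?** Two readings are possible.
- The outcome is log %BMIp95 at each visit. Change over time must then come from a visit term, and a difference between arms from arm-by-visit. Neither is listed.
- The outcome is one log-scale change per participant, to week 24 as in the preceding sentence. Months 3, 12 and 18 then do not enter at all.

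On either reading no arm contrast is produced.

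**3. Which adjusted scores are mediators?**
- YFAS-c: named a mediator and measured at all visits.
- BRIEF-2: named a mediator, but baseline only in the key-measures table and in its Measurements entry (the Outcomes table shows every visit). A baseline-only score cannot mediate.
- PSS: a covariate in the Outcomes table.
- CES-D and BEDS-7: absent from that mediator block. The key-measures table puts them under a heading that merges secondary outcomes with mediators.

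Only YFAS-c is both named as a mediator and clearly repeated.

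**4. What the timing of YFAS-c would do to an added arm term**

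Inputs from the power section: "a 92% power to detect an effect size of 0.625 corresponds to the mean difference of pre and post change in %BMIp95 at least 4.08" points, AppCoach against Clinic. Implied SD of change = 4.08 / 0.625 = 6.53. A two-sample t-test at two-sided 5% with 60 per arm (the size in the Statistical Analysis section) gives 92.4%, which reproduces the stated 92%.

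Assumptions that are not in the documents: mediated share s = 0, 25% or 50%; arm effect on the mediator 0.5 SD. The mediator slope is then b = s × 4.08 / 0.5, that is 0, 2.04 or 4.08 points per SD.

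Expected arm coefficient:
- with the baseline score: 4.08, whatever s is, because randomization makes baseline scores independent of arm;
- with the post-baseline score: (1 − s) × 4.08 = 4.08, 3.06, 2.04.

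A simulation of 3,000 two-arm trials with 60 per arm agrees:

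| s | Baseline score | Post-baseline score | Power with post-baseline score |
|---|---|---|---|
| 0 | 4.11 | 4.11 | 92% |
| 25% | 4.09 | 3.07 | 74% |
| 50% | 4.08 | 2.05 | 57% |

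Hand check at s = 25%: residual SD = √(6.53² − 2.04²) = 6.20; SE = 6.20 × √(2/60) × √1.0625 = 1.17, where 1.0625 = 1 + 0.5²/4 allows for the correlation between arm and mediator; 3.06 / 1.17 = 2.62; power ≈ Φ(2.62 − 1.98) = 74%.

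**5. What baseline adjustment gains**

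The power section assumes a pre-post correlation of 0.5. With outcome variance σ² at each time:
- change score: 2σ²(1 − 0.5) = 1.00σ²;
- follow-up adjusted for baseline: σ²(1 − 0.5²) = 0.75σ².

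On the plan's own assumption, adjustment alone removes a quarter of the variance of the change-score ANOVA.

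**The case against.** The strongest reply is that the document does contain an 18-month comparison. The power section names it, pairs it with ANOVA and t-tests, and names both pairwise contrasts; the Statistical Analysis section says the analyses accord with the planned protocol. A reader might also say that the mixed models were never meant as efficacy models. They assess associations with characteristics, so the scores are predictors of interest and the absence of an arm term is no fault. The wording on possible factors and other characteristics is open-ended and could include arm. Finally, ANOVA or t-tests at each visit would close the gap without a new model.

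Much of this stands. The association models are legitimate for their own purpose. It is right to say that they list no arm or visit term, not that they cannot contain one. The calculation in step 4 concerns a model the plan does not propose.

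It does not remove the gap. Tests named as the basis for power leave the analysis model, covariates and reported contrasts unspecified, and months 3 and 12 appear in neither section. A primary contrast that has to be read into an open-ended phrase is not prespecified. Tests at each visit would be a minimal repair, but on unadjusted change scores they would forgo the variance reduction in step 5.

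**Conclusion.** The point holds in this form: the analysis section specifies no between-arm estimate of %BMIp95 at 3, 12 or 18 months, although the Outcomes section makes those comparisons primary and the power section covers 18 months. This rests on the text alone and needs no numerical assumption.

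The YFAS-c point is conditional. It needs an arm term to be added, post-baseline values to be used, and real mediation. The figures of 3.1 and 2.0 points illustrate assumed shares; they do not forecast this trial.

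Three stronger readings are tempting, and the documents do not support them:
- *The plan has a faulty repeated-measures efficacy model.* The text states neither repeated measures nor the random effect, and describes an association model.
- *The model adjusts for mediators and so is biased.* Only YFAS-c clearly fits that description, its timing is unstated, and baseline values would cause no such bias.
- *The trial will yield no 18-month arm estimate.* The data are to be collected and a comparison is named for power. What is missing is its specified analysis.

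**What to change.** 1. Specify an efficacy mixed model for %BMIp95, and likewise for zBMI, with arm, visit, arm-by-visit, baseline outcome, site, participant-level correlation and baseline-only covariates.
2. Report AppCoach-Clinic and AppCoach-App contrasts at months 6 and 18, and report months 3 and 12 as well.
3. Keep the existing characteristic-association models as secondary. State their random effect and whether each score is a baseline or follow-up value.
4. Put post-baseline YFAS-c and FCQ in a separate mediation analysis.
5. Reconcile the BRIEF-2 schedule between the Outcomes table and the two places that make it baseline only.

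The cost is extra SAP text and code; the protocol already schedules the data. The Statistical Analysis section is written in the past tense, so if the week-24 analyses are already done, the new model must be labelled as added afterwards and the week-24 ANOVA reported beside it.
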